7.1.3 Phone Visit 1: (following a day after lumbar puncture)

- Study staff phone call to address AEs/SAEs Day 2 (+ 1 days) after visit 2/LP procedure
- There will be screening questions related to headache, bleeding at the site, and infectious symptoms.

7.1.4 Follow-up Visit 3 (Within a week of Visit 2 \pm 5 days).

The following procedures will be performed at this visit: This can be divided into two parts, with virtual and in-person visits

- Collect concomitant medication information and record AEs/SAEs
- Physical/neuro examination including examination of nares and nasal passages
- Collect vital signs, weight
- Pregnancy test for women of childbearing potential
- Review guidance on the use of effective birth control from the time of study enrollment until 30 days study **after** the final visit.
- 12-Lead Standard ECG
- C-SSRS
- Blood draw for laboratory investigations

7.1.5 Ad hoc Visit if Symptomatic:

- Collect vital signs, Weight
- Physical Examination
- Study staff to address AEs/SAEs

7.2 Early Withdrawal

If subject withdraws from the study after the screening visit, but before the lumbar puncture visit, no further evaluations are necessary.

7.3 Safety

For all safety assessments described below, any clinically significant change will be recorded as an adverse event (AE) or serious adverse event (SAE).

7.3.1 Physical Examination

Complete physical examination including examination of the nares/nasal passages will be performed at visits 1 and 3, or if the subject withdraws or is withdrawn from the study early. Any abnormalities noted at Visit 1, will be documented as part of the subject's medical history.

7.3.2 Neurological Examination

Neurological examination will be performed at visits 1, 3 or if the subject withdraws early. Any abnormalities noted at Visit 1, will be documented as part of the subject's medical history.

7.3.3 Vital Signs:

Vital signs will be recorded at all three study visits. Diastolic blood pressure will be measured at the disappearance of Korotkoff sounds. Vitals sign will be monitored by clinical staff during screening and lumbar puncture visits of the study.

Serum Glucose will be examined at visit 1 (screening) and visit 3 (safety follow-up). Fingerstick glucose tests will be performed at visit 2 (LP procedure). A blood glucose < 70 mg/dL will be considered clinically significant. The likelihood of peripheral hypoglycemia is low based on numerous clinical trials performed showing no effects of INI on peripheral glucose.

7.3.4 Weight:

Body weight will be measured at all three study visits.

7.3.5 Laboratory Samples:

All the laboratory samples will be drawn independent of fasting or non-fasting status.

When a patient withdraws from the study, samples collected prior to the date of withdrawal may still be analyzed, unless the patient specifically requests that the samples be destroyed or local laws require destruction of the samples. However, if samples have been tested prior to withdrawal, results from those tests will remain as part of the overall research data. Samples will be collected and processed according to the standard procedures. Key planned labs include:

- Basic Metabolic Panel
- Complete Blood Count
- Blood Coagulation Tests

7.3.6 Point-of-Care Glucose Testing:

At Visit 2, the participant will receive a single dose of intranasal insulin administered prior to their lumbar puncture. Point-of-care fingerstick glucose testing will be performed once before the administration of the study drug (baseline glucose reading) and twice after the administration of the drug according to the following schedule:

- (1) 15 minutes after study drug dosing (between the 2nd and 3rd CSF/serum samples are collected)
- (2) 45 minutes study drug dosing (after the final CSF/serum samples are collected)

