4.3 Safety

- Incidence and severity of serious adverse events (SAEs) and adverse events (AEs)
- Frequency of change in clinically-significant vital signs
- fingerstick glucose level <70mg/dl

5 Study Design

This Phase 1 is a single center, open-label, randomized pharmacokinetic study designed to describe the central nervous system delivery of intranasal insulin to CSF using anIN delivery device.

Table 1: Study Design

INI Insulin Dose	Collection Times
40 IU (n=6) 2 x 200 μ L (0.2ml)	0, 10, 20, 30, 40 min
80 IU (n=6) 2 x 200 μ L (0.2ml) Wait 2 min 2 x 200 μ L (0.2ml)	0, 10, 20, 30, 40 min

After written informed consent has been obtained, subjects will be screened to assess study eligibility based on study inclusion/exclusion criteria. Subjects who are eligible at the end of the screening visit will be randomized and assessed for outcome measures, including lumbar puncture and CSF/blood draw following a single dose of INI administered by the trained research staff. Randomization will be stratified by gender to ensure a balanced distribution of male and female participants within each group. A Block randomization scheme will be employed to ensure that the final group sizes are equivalent.

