7.1 Demographic and Baseline Assessments

7.1.1 Screening Visit 1

The following procedures will be performed at this visit: This may also be divided into two parts, with virtual and in-person visits. Virtual activities (e.g., consent, review of medical history/medications) can be completed on a separate day(s) from other study procedures, provided that consent occurs within 3 months of the lumbar puncture and all other screening activities are completed within the specified window (21-7 days prior to lumbar puncture visit/Visit 2). All activities will take approximately 2 hours to complete. No study procedures, virtual or otherwise, will be completed until a fully executed consent form has been obtained. Participants will be given the option to have a dose of sterile saline administered by research staff using the device if they want to experience the sensation of the device before the lumbar puncture visit.

- Obtain written informed consent Review Inclusion/Exclusion Criteria
- Review medical history, as it pertains to inclusion/exclusion criteria
- Pregnancy test for women of childbearing potential
- Review guidance on the use of effective birth control from the time of study enrollment until 30 days **after** the final visit.
- Obtain subject's demographic information (date of birth, gender, race, and ethnicity).
- Collect vital signs, height and weight
- Obtain details of medications taken over the course of the last 30 days
- Physical/neuro examination including examination of the nares and nasal passages
- Blood draw for laboratory investigations
- C-SSRS
- 12-Lead Standard ECG
- Saline test dose (optional)
- Pre-procedure instructions
- Provide Information sheet provided relating to pre-lumbar puncture hydration
- Visit #2 scheduled after 2 weeks \pm 7 days

7.1.2 Lumbar Puncture Visit 2: In-Person Visit (2 week \pm 7 days after Visit 1)

The subject will be check in at the Regions Hospital outpatient care unit (OPCU). The visit will be at the General Radiology Department (where the lumbar puncture will be performed and study data collected) and will return to the OPCU for post-operative monitoring.

The following procedures will be performed at this visit:

- Review Inclusion/Exclusion Criteria
- Collect concomitant medication information and record AEs/SAEs
- Collect vital signs and weight
- Pregnancy test for women of childbearing potential
- Review guidance on the use of effective birth control until 30 days study **after** the final visit.

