7.1.2.1 Fluoroscopy-Guided Lumbar Puncture Procedure

CSF samples will be collected according to standard operating procedures for fluoroscopy-guided lumbar puncture as observed by the General Radiology department at Regions Hospital. The procedure will be performed by a trained clinician (i.e., an interventional radiologist or an experienced member of their team), who will obtain verbal consent (in addition to the research informed consent obtained/documentated at Visit 1). CSF will be collected serially using gravity drainage. Sterile extension tubing connected to the LP needle will dispense CSF into sterile collection tubes for pharmacokinetic analysis. Samples will be collected at 5 times: once prior to the administration of a single dose of intranasal insulin and at once each at 10, 20, 30, and 40 minutes post-drug administration. Approximately 1-2ccs of CSF will be collect at all 5 time points for a total of 10ccs of CSF. The tubing connected to the needle will be flushed out between sample collections to avoid contamination between specimen timepoints. The subject will lie in prone position throughout the procedure with appropriate measures taken to minimize discomfort (e.g., provision of warm blankets, use of positioning sponges, etc.).

Subjects will lie on their back 2 hours after the procedure for standard-of-care monitoring with nursing staff, and periodic collection of vital signs. Participants will receive instructions from the clinical team on techniques for preventing and treating post-LP headache (e.g., drinking water and caffeinated beverages, using over-the-counter pain medications). They will also receive guidance on when to seek additional help for their headache and/or any other emergent symptoms requiring immediate medical attention such as fever, persistent headache, and weakness/numbness of the lower extremities. Subjects will receive a safety assessment phone call from study staff 1 day after the procedure.

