7.3.11.2 Serum Samples

It is our intention to collect samples at pre-defined times following a single dose administration. Serum will be collected at 0, 10, 20, 30 and 40 minutes for all study participants. Serum samples will be assessed for insulin using the same one-step sandwich immunoassay with a limit of detection of 0.1 µIU/ml or 0.7 pmol/L.

Table 2: Study Visit Schedule

Assessment/ Procedure	Visit 1: Screen	Visit 2: Lumbar Puncture (LP)	Phone Visit 1: Safety Check	Follow-up Visit 3	Ad Hoc Visit if Symptomatic
Schedule – Week and Windows	-2	1	Following day after LP	Within 1 week of Visit 2	
		± 7 days	+ 1 day	± 5 days	
Informed consent	X				
Review of inclusion/exclusion criteria	X	X			
Medical History, demographics	X				
Physical/Neuro exam with examination of nares and nasal passages	X			X	X
Vital Signs (Blood pressure, heart rate, weight)	X	X		X	X
Height	X				

Basic Metabolic Panel (Na, K, CO ₂ , CL, BUN, Creatinine, Glucose and Ca)	X			X	
Labs INR/PT/PTT	X			X	
Complete Blood Count	X			X	
Pregnancy Test (in females)	X	X		X	
Counseling on effective birth control	X	X		X	
Randomization		X			
Lumbar Puncture		X			
Glucose Finger Stick (0 Min, 15 Min, 45 Min)		X			
Nasal Irritation Scale (0, 20, 40 min)		X			
CSF Samples and Insulin Levels (0-40 Min)		X			
Serum insulin Levels (0-40 Min)		X			
C-SSRS, 12-Lead Standard ECG	X			X	
Pre-Procedure instructions	X				
Study Drug Administration (single dose)		X			
Concomitant Medication	X	X	X	X	X
Adverse Events	X	X	X	X	X

8 Investigational Product(s)

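### No visible meal condition for the Visit 2 insulin samples: endogenous insulin adds noise to the serum results and can mimic or hide a within-arm dose effect

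*Combined protocol and SAP*

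**What the plan says.** Section 3.2 sets the secondary objective: to describe what one intranasal dose does to serum insulin. Section 4.2 makes the endpoint serum insulin levels over 0-40 min. Section 7.3.11.2 gives the schedule ("Serum will be collected at 0, 10, 20, 30 and 40 minutes for all study participants") and the method ("Serum samples will be assessed for insulin using the same one-step sandwich immunoassay"), so there is one pre-dose value per participant. The Protocol Summary names regular human insulin as the drug and lists no control. Section 5 assigns 6 participants to 40 IU and 6 to 80 IU, stratified by gender only: "A Block randomization scheme will be employed to ensure that the final group sizes are equivalent". Section 12.2 plans individual line graphs, mean ± SE, Cmax, Tmax and AUC for CSF, and a similar analysis for serum. It states no baseline correction.

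On meal state, the only visible statement is in 7.3.5: "All the laboratory samples will be drawn independent of fasting or non-fasting status". The tests named there are the metabolic panel, blood count and coagulation tests, which Table 2 (Study Visit Schedule) places at Visits 1 and 3. The Visit 1 list in 7.1.1 includes pre-procedure instructions, whose content is not given, and separately a hydration sheet: "Provide Information sheet provided relating to pre-lumbar puncture hydration". For the lumbar puncture, 7.1.2.1 refers to hospital procedures ("CSF samples will be collected according to standard operating procedures for fluoroscopy-guided lumbar puncture") and adds "The subject will lie in prone position throughout the procedure".

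**The concern.** The endpoint is the concentration of a hormone that participants also make themselves, in amounts that depend on when they last ate. If participants arrive in different meal states, two separate problems follow.

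- **Level.** A recently fed participant can start well above a fasted one. Without baseline correction, that difference goes straight into Cmax, AUC and the arm mean, and widens the SE.
- **Drift.** Endogenous insulin may still be rising or falling over the 40 minutes. Subtracting the 0-min value removes level but not drift. Drift in a common direction shifts both arms together, so randomization does not remove it from the within-arm description.

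The stake is how the secondary objective is read. Section 1.1.3 reports no significant change in circulating insulin at 40 IU and only a small detectable increase in some studies at 160 IU. Against a signal that small, modest drift could be taken for a drug effect or could cancel one.

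**Working it through.** The plan has no figure to reproduce: it gives no SD, no effect size, and no fed or fasting insulin values. The check is therefore a reading of the text, followed by illustrations in which every insulin input is assumed.

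**1. The text.** The Visit 2 procedure list (7.1.2), the sampling section (7.3.11), Table 2 and the analysis section (12.2) contain no fasting rule, standard meal or last-meal record. If 7.3.5 covers the insulin samples, any meal state is allowed; if it covers only safety labs, the insulin samples have no visible rule. The gap remains either way.

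**2. Drift alone, no drug effect.** Let serum insulin, relative to its own pre-dose value, be s(t) = 1 + (f - 1)t/40 at 0, 10, 20, 30 and 40 min, where f is the fold reached at 40 min. By the trapezoid rule AUC/40 = 1 + (f - 1)/2. The baseline-corrected mean is (f - 1)/2, and Cmax = max(1, f).

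| f | Corrected mean, % of baseline | AUC v flat profile | Cmax v baseline | Tmax |
|---|---|---|---|---|
| 0.5 | -25 | 0.75x | 1.0x | 0 min |
| 1.5 | +25 | 1.25x | 1.5x | 40 min |
| 2.0 | +50 | 1.50x | 2.0x | 40 min |

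**3. Six participants per arm.** If f is uniform from a to b, the mean shift is ((a + b)/2 - 1)/2, the SD is (b - a)/(2√12), and the SE per arm is SD/√6. The SE of the difference between arms is √2 times that.

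- f from 0.5 to 2: shift (1.25 - 1)/2 = +12.5%; SD 1.5/(2√12) = 21.7 points; SE 8.8 per arm; SE of the dose difference 12.5, with expected difference 0.
- f log-uniform from 0.5 to 2: mean f = 1.5/ln 4 = 1.082, shift +4.1%, SE 8.7.
- All falling, 0.5 to 1: shift -12.5%, SE 2.9.
- All rising, 1 to 2: shift +25%, SE 5.9.
- Near-stable insulin, 0.9 to 1.1: shift 0, SE 1.2 per arm and 1.7 for the difference.

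These are percentages of each participant's own baseline, not the mean ± SE of concentration that 12.2 plans. They leave out differences in level, which come next.

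**4. Level and drift together.** Assume a fasted level of 5 µIU/mL and, in a fed participant, C(t) = 5 + (B - 5) × 0.5^(t/h), where B is the pre-dose value and h the half-time of decline. For B = 40 and h = 40 min, the five values are 40, 34.43, 29.75, 25.81 and 22.5. The AUC is 10 × (40/2 + 34.43 + 29.75 + 25.81 + 22.5/2) = 1212 µIU·min/mL, against 5 × 40 = 200 fasted. After subtracting the baseline it is 1212 - 40 × 40 = -388.

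With one such participant among six, the uncorrected arm mean is (5 × 200 + 1212)/6 = 369 instead of 200. The corrected arm mean is -388/6 = -65 instead of 0. Correction removes the inflated level and leaves the fall.

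**5. Chance imbalance.** If each participant independently arrives fed with probability 0.3 to 0.7, sum Bin(6, p) × Bin(6, p) over pairs of counts that differ by at least 2. The two arms then differ by 2 or more fed participants with probability 0.34 to 0.39, and by 3 or more with probability 0.11 to 0.15. This is noise in the dose contrast, not bias.

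**The case against.** The case on the other side has real force.

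- *The 7.3.5 sentence is probably about safety labs.* This stands as a caution. A reader might infer that the plan deliberately takes the insulin samples in any meal state; its position and its list of tests do not support that. What remains is silence on the insulin samples.
- *A rule may exist out of sight.* It could be in the pre-procedure instructions, the hospital lumbar puncture procedures, the redacted 5.3.1-5.3.2 or the redacted Appendix F. Section 13.7 says the CRFs are developed internally, and they are not in the file, so last-meal time may already be captured. The point is therefore limited to visible text, and a citation would answer that part.
- *The dose effect need not be read from the change alone.* This is correct. The randomized 40 v 80 IU contrast also bears on it and stays unbiased in expectation. It does not show what either dose does compared with no dose.
- *Simply requiring a common meal condition would not cure drift.* This is also correct: a shared fed state could produce the very shift described. The condition has to be one under which endogenous insulin is expected to be stable.
- *Safeguards are already planned.* Individual profiles and fingerstick glucose at 0, 15 and 45 min may reveal a gross fed pattern. They are an indirect check, not a meal record. Eating during sampling is implausible because participants lie prone, so only an earlier meal matters. Check-in and needle placement before the pre-dose sample make a still-rising curve less likely, though no durations are given.
- *The endpoint is secondary and descriptive, in 12 people.* True, and it limits the weight of the point.

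**Conclusion.** The point holds as a cheap improvement. As visibly written, the plan lets differences in endogenous level add variance to uncorrected serum Cmax and AUC. It also lets post-meal drift mimic or hide a within-arm effect on serum insulin. This rests on three facts (human insulin, no undosed arm, no stated baseline correction) and on the assay not being stated to separate endogenous from administered insulin.

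The size is unknown. The range of -25% to +50% of baseline, and the SE of 12.5 points for the dose difference against 1.7 with near-stable insulin, follow from assumed folds and would change with them.

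Three stronger readings are not supported. The 40 v 80 IU comparison is not biased, because doses are randomized; it is only noisier. No harm to the primary CSF endpoint is shown: nothing in the documents quantifies how meal state would carry into CSF within 40 min, and the effect may be zero. No error rate or power is at stake, because the plan contains no test.

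**What to change.** 1. **Section 12.2.** Report serum insulin also as change from the 0-min value, including baseline-corrected Cmax and AUC, and state that this removes level differences but not drift. Keep the uncorrected results beside it, since the single 0-min sample carries its own error.
2. **Section 7.3.11.** State one meal condition for all participants under which endogenous insulin is expected to be stable over 0-40 min, or cite it if an existing instruction already sets one. Reconcile 7.3.5 with it. The sponsor's clinicians choose the condition, consistent with 13.2.1; none is proposed here.
3. **Visit 2 CRF.** Record time of last meal if the form does not already. Read the serum profiles alongside it and the planned 0, 15 and 45 min glucose readings.

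Cost: a sentence in 7.3.11, a clarification in 7.3.5, at most one CRF field, and one more descriptive summary from data already planned. No new samples or visits are needed. The downside is a small scheduling burden and a brief clinical check of the chosen condition against the glucose rules in 13.2.1. Items 2 and 3 need to be settled before dosing, because last-meal time cannot be reliably recovered afterwards.

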7.3.7 Pregnancy Test

All women of childbearing potential will have blood collected to test for pregnancy. This will be performed at the screening visit (Visit 1), treatment visit (Visit 2), and final follow-up visit (Visit 3). A negative pregnancy test (urine) must be confirmed on the day of Visit 2 prior to the administration of the study drug.

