7.3.11.1 CSF Sampling

It is our intention to collect samples at pre-defined times following a single dose administration. CSF will be collected at 0, 10, 20, 30 and 40 minutes for all study participants. CSF samples will be assessed for insulin using a one-step sandwich immunoassay with a limit of detection of 0.1 µIU/ml or 0.7 pmol/L

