8.4 Occupational Safety

No known significant safety risks exist to site personnel in direct or indirect contact with the study drug. As the lumbar puncture will employ fluoroscopy, clinical (non-research) staff will be exposed to radiation. The fluoroscopy technicians and radiologist will follow standard clinical protocols for radiation safety (e.g. wearing lead Personal Protective Garments). The amount/duration of radiation exposure for this research LP is not greater than what would be experienced during a routine LP. As fluoroscopy is only needed to assist with needle placement, study staff will not need to be present for this part of the procedure and can step out of the procedure room while the fluoroscopy machine is in use. Research staff can then reenter the room to assist with pre-dose sample collection/fingerstick glucose testing after the machine has been deactivated.

9 Concomitant Medications and Non-Drug Therapies

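### The Visit 2 pregnancy result is due only before dosing (7.3.7), but most of the protocol puts fluoroscopy and lumbar puncture before dosing, while 7.3.6 says the reverse

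*Combined protocol and SAP*

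**What the plan says.** **The deadline.** Section 7.3.7 begins "All women of childbearing potential will have blood collected to test for pregnancy" and assigns a test to each of the three visits. It then sets the Visit 2 rule: "A negative pregnancy test (urine) must be confirmed on the day of Visit 2 prior to the administration of the study drug".

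**The order of puncture and dose.** Section 7.1.2.1 states "Samples will be collected at 5 times: once prior to the administration of a single dose of intranasal insulin", with the other four samples at 10, 20, 30 and 40 minutes after it. CSF drains through tubing attached to the lumbar puncture needle. Section 7.3.11.1 gives the same schedule: "CSF will be collected at 0, 10, 20, 30 and 40 minutes for all study participants". Section 8.4 says of the imaging "As fluoroscopy is only needed to assist with needle placement", lets study staff leave for that step, and continues "Research staff can then reenter the room to assist with pre-dose sample collection/fingerstick glucose testing after the machine has been deactivated".

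**The contrary statement.** Section 7.3.6, on point-of-care glucose, says that at Visit 2 "the participant will receive a single dose of intranasal insulin administered prior to their lumbar puncture".

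**Eligibility.** Inclusion criterion 5 (6.1.1) requires a negative test at both the screening and the treatment visit, unless the participant is post-menopausal or surgically sterile. Exclusion 6 (6.1.2) bars pregnant participants. The Visit 2 list in 7.1.2 opens with a review of the eligibility criteria and names the pregnancy test above the lumbar puncture.

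**The concern.** A check that decides eligibility would be expected to finish before the procedures that depend on it. The participants are healthy volunteers, so the fluoroscopy and the puncture are done for the research alone. If both come before the dose, a rule tied to the dose lets a site comply with 7.3.7 while learning the result only after the participant has been imaged and punctured. At stake are participant protection and an instruction that staff can follow without guessing. No estimate or analysis depends on it.

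**Working it through.** The plan gives no figure to reproduce here. The check is a reconstruction of the Visit 2 order, plus one date calculation.

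**1. Order from 7.1.2.1, 7.3.11.1 and 8.4.**
- Fluoroscopy serves needle placement (8.4).
- The machine is switched off and research staff come back for the pre-dose sample and fingerstick (8.4).
- The first of five CSF samples is taken through the needle, before the dose (7.1.2.1). It is the 0-minute sample of 7.3.11.1.
- The dose is given. The 7.3.7 deadline falls here.
- CSF is taken at 10, 20, 30 and 40 minutes.

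On this order, a result that arrives after the puncture but before the dose satisfies 7.3.7.

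**2. Order from 7.3.6.** Dose first, then lumbar puncture. On this order the 7.3.7 deadline falls before the puncture, and the gap closes.

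**3. Can both orders hold?** No. The protocol describes one puncture with serial collection. If the dose came first, all the CSF from that puncture would be post-dose, and 7.1.2.1 could not have its pre-dose sample. Section 7.3.6 also places its 15-minute fingerstick between the second and third samples. That fits samples at 10 and 20 minutes, so 7.3.6 itself uses the five-sample schedule whose first sample 7.1.2.1 puts before the dose.

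**4. Is there another deadline within Visit 2?**

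| Place | What it fixes | Time within Visit 2 |
|---|---|---|
| 6.1.1, criterion 5 | Negative test at the treatment visit | None |
| 7.1.2 list | Test named above the puncture | None, and no statement that the list is chronological |
| Visit schedule table | Test marked at Visit 2 | None |
| 7.3.7 | Negative urine test, same day | Before study drug |

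The 7.1.2 list also puts dosing below the whole CSF and serum series, so it is not a strict sequence throughout.

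**5. Age of the previous test.** Visit 2 is 2 weeks ± 7 days after Visit 1: 14 − 7 = 7 days and 14 + 7 = 21 days. This agrees with the 21-to-7-day screening window in 7.1.1. The Visit 2 test is therefore the only check less than a week old.

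**The case against.** The case for leaving the text alone has real force. Criterion 5 makes a negative treatment-visit test a condition of inclusion. Exclusions 6 and 7 bar pregnancy and any safety factor that precludes lumbar puncture. Eligibility review is the first item on the Visit 2 list, and the pregnancy test stands above both the clinician's discussion and the puncture. The misplaced dosing item does not show that the preparatory items are out of order. A latest limit at dosing is compatible with testing on arrival. The puncture also follows the radiology department's own operating procedures, which may contain a pregnancy check; they are not in the documents.

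This shows that early testing is probably intended. It does not supply a deadline for the result, and the one sentence that does is tied to the dose.

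A reader might infer more than the text supports:
- *That the plan lets a participant of unknown status go to fluoroscopy as a matter of course.* The eligibility criteria and the list point the other way. The gap is in the stated deadline.
- *That a late positive result would cost the trial a participant who could not be replaced.* Section 10.2 also provides for replacing subjects without sufficient samples, and a participant stopped before dosing would reasonably fall under it.
- *That about 6 of the 12 are exposed.* Stratifying by gender balances the sexes between arms. It does not fix the share of women, so the figure would be an assumption. Actual harm would also need a result that is both late and positive.
- *That the qualifying specimen is unspecified.* The deadline sentence names urine. What remains is a mismatch with the preceding sentence, which speaks of blood.

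**Conclusion.** The point holds as a sequencing inconsistency. The only explicit Visit 2 deadline can be met after radiation exposure and puncture on the order given by 7.1.2.1, 7.3.11.1 and 8.4. Section 7.3.6 gives the reverse order, and the two cannot both stand.

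The rule reaches every participant of childbearing potential, a number the protocol does not state. No endpoint, sample size or analysis changes. The amendment is worth making because it bears on the protection of healthy volunteers and costs little.

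The conclusion assumes that the 0-minute CSF sample of 7.3.11.1 is the pre-dose sample of 7.1.2.1. It concerns the protocol text only: what the radiology department's procedures require, and what the site does in practice, cannot be judged from these documents.

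**What to change.** Reconcile 6.1.1, 7.1.2, 7.1.2.1, 7.3.6, 7.3.7 and 8.4 on the order of three things at Visit 2: confirmation of eligibility (including the pregnancy result), fluoroscopy and lumbar puncture, and dosing. The sponsor and investigator should settle that order. The 7.3.7 deadline should then agree with it and with the eligibility criteria, and 7.3.6 should no longer contradict the pre-dose CSF sample. Amending 7.3.7 alone would leave that contradiction in place. In the same amendment, align the blood and urine wording within 7.3.7.

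The cost is a short wording change. The test is already done at Visit 2, so the only operational effect is a possible short wait for the result.
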